### **Methods**

Trial design	3a	Description of trial design (such as parallel, factorial) including allocation ratio	When applicable, how care providers were allocated to each trial group
--------------	----	--	--

3b	Important changes to methods after trial commencement (such as eligibility criteria), with reasons	Definition of cluster and description of how the design features apply to the clusters:
----	--	---

A 2 x 2 cluster-randomized cross-over trial at subject level was conducted to evaluate the effect of a 40-day organic diet compared to a 40-day conventional diet on biomarkers of exposure (pesticides metabolites) and biomarkers of effect (oxidative stress/inflammation markers) in children. The study was conducted in six randomly selected primary schools (clusters) with two periods (organic and conventional) in Limassol, Cyprus between January and April 2017. The trial was approved by the Cyprus National Bioethics Committee (EEBK/ΕΠ/2016/25) and the Cyprus Ministry of Education and Culture (7.15.06.15/2). The schools were *a priori* randomized to one of two groups differing only on the sequence of the treatments; organic diet - conventional diet (Group 1) and conventional diet-organic diet (Group 2). The ratio of Group 1: Group 2 participants was 1:2.5.

The reasons for this cluster randomization were: (1) to avoid the transfer of knowledge within schools about the organic diet intervention from children randomised in the intervention arm to children randomised in the conventional arm (contamination effect); (2) to enhance compliance, since all participating children at a given school would follow the same intervention; (3) more efficient delivery of the organic meals during the organic period since the organic meals-preparing restaurant would daily deliver meals to 3 instead of 6 schools.

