Descriptive statistics were used to summarize the demographic and other characteristics of participating children. Categorical variables were described with frequencies and percentages, normally-distributed continuous variables as mean $\pm$ SD and non-normal continuous variables as median and interquartile range (25th-75th percentiles). Box plots were used to visually inspect the biomarker data. For data below LOD, imputation was performed based on existing suggestions for handling non-detect data. For 6-CN and 3-PBA, the percentage of data below LOD was 72% and 23% accordingly, so the imputation was performed using the regression on order statistics (ROS). For MDA and creatinine, the percentage of data below LOD was very low ( $\approx$  1%), so the LOD/2 imputation was used. The baseline characteristics were compared between the study groups with t-test for the normal continuous variables or Wilcoxon test, and chi-square for the normal, non-normal, and for the categorical variables, respectively.

The percent change between the baseline (last sample of conventional treatment before the start of the organic treatment) and after 40 days of organic diet (last sample of organic treatment) was determined with one sample t-test for all biomarkers (log-transformed) and the change between the conventional and organic treatment (medians) was determined using Wilcoxon test for all biomarkers (non-normal variables).

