restaurant was responsible for the preparation and provision of organic meals for all schools during the organic period helping ensure that the treatment was comparable per the stable unit treatment value assumption (SUTVA). Informed consent was obtained at school level by the headmaster of the participating school, followed by written informed consent that was obtained from each participating children's parents or legal guardians.

Objectives

The primary objective of the ORGANIKO LIFE+ trial was to determine the effectiveness of an organic diet intervention in reducing the body burden of urinary concentrations of pyrethroid and neonicotinoid pesticide metabolites in children aged 10-12 years in Cyprus.

The secondary objective of this trial was to evaluate the effect of an organic diet intervention on urinary biomarkers of oxidative stress/inflammation (OSI).

Inclusion and exclusion criteria

Inclusion criteria for clusters

Public primary schools within the urban area of Limassol.

Inclusion criteria for participants

Healthy children (males and females) at the age of 10-12 years old, attending public primary schools in Limassol, residing in Cyprus at least for the last five years and systematically consuming conventional food (>80% of the week's meals).

Exclusion criteria for participants

Children with chronic conditions (e.g. diabetes, asthma) or allergies in food (e.g. gluten, lactose tolerance).

Randomization and blinding

The unit of randomization was the school. Schools were randomly assigned following simple randomization procedures of no restriction or matching (computerized random numbers) to 1 of 2 groups depending on the sequence of the treatments (Group 1 and Group 2). Simple randomization was performed by a computer generated random list that was prepared by an investigator with no clinical involvement in the trial. A member of the research team enrolled participants after knowing the allocation sequence for

each school since parents and children had to be informed of the order the intervention was going to take place.

Participants of schools in Group 1 began first with the organic period and continued with the conventional period whereas participants of schools in Group 2 began first with the conventional period and then switched to the organic period.

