The blinding of the participants to group assignment was not possible with the present study design. The blinding of the researchers to the subjects' identity was achieved by the coding of all study materials (urine containers, questionnaires, and diaries). The study personnel who obtained the outcome measurements were also not informed of the group assignment. The personnel who delivered the intervention did not take any outcome measurements. All outcome assessors and data analysts were kept masked to the allocation.

Recruitment process

Following the bioethics approval of the study, twelve primary schools' headmasters were randomly selected and contacted by the study coordinator. Six schools accepted to implement the study.

Informational flyers were offered to parents and information meetings were arranged to present study-relevant details and to provide additional study materials for their review (menus, details of study, interest forms, consent forms for the parents/guardians of the participating child, and forms for breakfast and afternoon snack options). Parents that could not attend the meeting received the relevant material at home through the schools. Similar meetings, although using different study materials, were arranged with children in each school to inform them about the study, to explain to them the definition of organic food products (raw and processed), and to have them taste organic fruits. The importance of compliance to the study protocol was highlighted to both parents and children and the ways to report it in a diary, including examples of proper use. The research team checked if all eligibility criteria were satisfied, using the completed interest forms, and parents were accordingly informed via telephone. Following, informed consents were signed by parents of the children that were willing to participate. Bags containing six coded urine vials, sampling dates, instructions for urine collection, and the food diary were given to children or to their parents during school hours. The organic restaurant was selected based on a public tender procurement procedure with some of the requirements being the use of 100% certified organic raw

materials and food products, frequently renewed certificate for preparation of organic meals, and national accreditation for delivery of meals to schools, complying to ISO 22000 and HACCP protocols.

Intervention

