The baseline characteristics were summarized overall and by study group. These include: demographics, anthropometric measurements (waist circumference and BMI standard deviation scores (SDS)), days in organic period, total samples number, physical and sedentary activity time and frequency of food categories consumption. BMI SDS was calculated based on the measurements of weight and height, adjusting for age and sex, using the WHO 2007 growth reference standard for children.¹² Continuous variables were checked for normality with QQ plots and histograms. Categorical variables were described with frequencies and percentages, normally-distributed continuous variables with means and standard deviations, and non-normal continuous variables with medians and interquartile ranges (25th-75th percentiles).

Baseline data were tested for difference between both study groups by

- Chi-squared test for categorical variables
- T-test for normally distributed continuous variables
- Wilcoxon test for non-normally distributed continuous variables

Conventional period energy analysis

The diet of the children (self-reported food items consumption) during the conventional period was recorded using a food frequency questionnaire (ffq) that was administered to parents through telephone. The ffq was based on the Kafatos food frequency questionnaire^{13,14}, that was used originally in the Crete's population (Greek language). Kafatos was one of the key researchers accompanying [name] in the famous 7 countries study's publications¹³, where this FFQ questionnaire was validated and used in the Crete's population. Both Cyprus and Crete are Mediterranean, Greek-speaking islands in very close geographic and cultural proximity. The Kafatos FFQ was adapted accordingly to the Cypriot diet¹⁵ and was used in the Cyprus Research Promotion Foundation study called Cyprus Metabolism Study on 18 yrs. old male soldiers (n=1100) (CYACCESS prospective study).

The mean daily energy intake of the participants was calculated based on a table, that was provided by a registered dietitian and which reported the energy (kcals) of each food item included in the questionnaire (see SAP Appendix).

Change between baseline and the end of the organic period

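### The baseline tests between sequence groups treat children as independent although six schools were randomised, so their p-values are too small whenever the school ICC is above zero

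*SAP*

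**What the plan says.** The SAP (Randomization and blinding) states: "The unit of randomization was the school". Under Recruitment process it adds: "Six schools accepted to implement the study". Allocation was unrestricted: "Schools were randomly assigned following simple randomization procedures of no restriction or matching".

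Under Baseline characteristics the SAP summarises the variables overall and by study group, and then: "Baseline data were tested for difference between both study groups by" chi-squared for categorical variables, "T-test for normally distributed continuous variables" and Wilcoxon for the rest. Protocol item 12 (Statistical methods) agrees: "The baseline characteristics were compared between the study groups with t-test for the normal continuous variables or Wilcoxon test", with chi-squared for categorical variables. No cluster term is named in either place.

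The primary models in both documents do carry a school-level random intercept to deal with clustering. Item 15 of the checklist in the protocol's Results section asks for baseline characteristics at both the individual and the cluster level, as applicable.

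**The concern.** Sequence group was assigned to schools, so the comparison of groups is a comparison among six units. The planned tests take their standard error from variation between children, as if each child had been allocated separately. Children at one school may share neighbourhood, habits and diet. The listed variables include demographics, activity time and food frequency, which may well differ by school. Any such similarity adds between-school variance that the tests leave out.

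The table carries some weight in this trial. Protocol items 9 and 10 and the SAP (Randomization and blinding) say that families were informed and enrolled once their school's sequence was known. The baseline table is therefore a natural place to look for selective uptake. An unclustered p-value cannot separate that from the ordinary differences between whichever schools fell into each group. The false discovery rate procedure in the SAP (Multiple testing) covers regression parameters of the primary and post-hoc analyses, so it does not reach these tests.

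**Working it through.** **Inputs from the documents.** Six schools; two-sided 5% level; planned 200 children; and "The ratio of Group 1: Group 2 participants was 1:2.5" (Protocol, item 3a). The planned number can be reproduced: n = (0.5 × (1.960 + 0.842) / 0.1)² gives 197 after rounding up, or 199 with the t distribution, and power at 200 is 80.4%. This takes 0.5 as the SD of the paired difference. The 200 is used below only as a cluster-size input.

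**Inputs that are assumptions.** The ICC is not given, so a range is used. Three schools per group is implied by the delivery rationale ("daily deliver meals to 3 instead of 6 schools") but is not stated as the allocation. The number analysed is not given, so 150 is tried as well.

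**Step 1, formula.** With m = 200/6 = 33.3 children per school, the design effect is DE = 1 + (m − 1) × ICC. The true false-positive rate of the unclustered test is 2 × [1 − Φ(1.96/√DE)]. For example:

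- ICC 0.01: DE = 1 + 32.3 × 0.01 = 1.32, rate 8.8%.
- ICC 0.05: DE = 2.62, rate 22.6%.
- ICC 0.10: DE = 4.23, rate 34.1%.

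**Step 2, simulation with unequal schools.** There were 20,000 simulated data sets per setting with no true group difference. For 200 children the school sizes were 19, 19, 19 against 47, 48, 48 (57:143, or 1:2.5). For 150 they were 14, 14, 15 against 35, 36, 36 (43:107). The chi-squared test was applied to a variable split at its median. The entries are percentages of null data sets with p < 0.05.

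| ICC | Formula, 200, equal schools | t-test, 200 | Chi-squared, 200 | t-test, 150 | t-test on six school means, 200 |
|---|---|---|---|---|---|
| 0 | 5.0 | 5.0 | 4.8 | 4.9 | 5.5 |
| 0.01 | 8.8 | 8.0 | 7.1 | 7.2 | 5.4 |
| 0.02 | 12.7 | 11.4 | 9.2 | 9.9 | 5.2 |
| 0.05 | 22.6 | 19.7 | 14.6 | 15.9 | 4.9 |
| 0.10 | 34.1 | 30.7 | 23.5 | 25.8 | 4.8 |
| 0.20 | 47.3 | 44.2 | 35.5 | 39.7 | 4.8 |

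In multiples of the nominal 5%, the t-test with 200 children runs from 8.0/5 = 1.6 at ICC 0.01 to 30.7/5 = 6.1 at ICC 0.10. Wilcoxon is close to the t-test (7.0% and 30.2% at those two ICCs, from 4,000 runs). A 2:4 split of schools at the same ratio gives 8.7% and 32.9% for the t-test. The t-test on school means stayed between 4.8% and 5.7% in every setting tried, so the excess comes from ignoring the schools.

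**Step 3, what a school-level permutation test could show.** Given a 3:3 split there are 20 allocations, and the smallest two-sided p-value is 2/20 = 0.10. Given 2:4 there are 15, and the smallest is 1/15 = 0.067. Over all 2⁶ = 64 unrestricted allocations it is 2/64, about 0.03.

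**The case against.** The strongest reply is that nothing depends on these p-values. Neither document uses them to choose covariates, define a population or change a model. The treatment contrast is largely within child, and the primary model has student and school intercepts and adjusts for the baseline outcome. This stands: a reader might infer that the trial's effect estimate is compromised, and the documents do not support that.

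Three other stronger readings should also be set aside.

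- A reader might take six times the nominal rate as a ceiling or as a property of this trial. It is neither. By the formula it corresponds to an ICC of about 0.08 with 200 children or 0.11 with 150, and the factor is larger at higher ICCs. The documents give no ICC.
- A reader might multiply a rejection rate by the number of table rows to count false flags. The SAP lists kinds of characteristic without a total, the ICC will differ between them, and categorical variables get the less inflated chi-squared test.
- A reader might conclude that no valid school-level test can reach 5%. The 0.10 floor belongs to a permutation test conditional on a 3:3 split, which is inferred here. A t-test on six school means holds its level in the simulations and can reject.

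Group is also not strictly a school attribute in the analysis. The SAP (Participant population) counts two children from Group 2 schools in Group 1. The tests remain unclustered all the same.

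**Conclusion.** The point holds as a minor one. The baseline tests ignore the unit of randomisation, and their p-values are too small for any positive school ICC. Assuming 3:3 schools, the 1:2.5 ratio and 200 children, the t-test's false-positive rate is about 8% to 31% for ICC 0.01 to 0.10, or 1.6 to 6 times nominal, and more above that. With 150 children it is about 7% to 26%. The direction is certain from the text. The size rests on an ICC, a school split and an analysed number that the documents do not supply. The consequence is confined to how the baseline table is read: a small p-value there may reflect no more than which schools fell into each group.

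**What to change.** Delete the baseline significance tests from the SAP (Baseline characteristics) and from protocol item 12. Present each characteristic by group and by school, which also supplies the cluster-level baseline data that checklist item 15 asks for. Add a footnote saying where the two children analysed outside their school's group are counted. Readers can then judge possible selective uptake from the size of the differences and their spread across schools.

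If a test is kept, make it a school-level one, for example a t-test on the six school means with 6 − 2 = 4 degrees of freedom. State that its power is low, so that a non-significant result is not read as evidence of balance. If a permutation test is used instead, report the actual school split and the smallest p-value it allows.

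The cost is one column removed from a table and one by-school summary added. No new data are needed, and the primary analysis is unchanged.

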Each school that participated in the study was *a priori* randomized to one of the two groups depending on the sequence of the treatments; organic-conventional (Group 1) and conventional-organic (Group 2). The order in which participants undertook the organic and conventional periods of the study depended on their school, hence the intervention randomization pertained to the cluster/school level. Schools in Group 1 began first with the organic period and continued with the conventional period whereas schools in Group 2 began first with the conventional period and then switched to the organic period. During the conventional period, participants were asked to maintain their usual dietary habits and choices (>80% conventional diet) for a total of maximum 40 days. The organic period was organized in two 20-day cycles with differences in the menu to allow for greater variety in the meals, so that the participants' compliance to the organic treatment would be enhanced. During the organic period, participants were asked to strictly follow the two 20-day organic dietary menus provided to them for a total of 40 days. The organic dietary menus were prepared by a certified dietitian based on EFSA energy requirements for children aged 10-12 years, and included five meals per day; breakfast, morning snack, lunch, afternoon snack, and dinner. The meals of the organic period were delivered to schools Monday to Saturday, except for Sunday. Upon arrival of daily meals to each school, the teachers and headmaster were responsible for handing the packages to each participating child, using a project participant list around lunch time. On Saturday, the food package included both the Saturday and Sunday meals; for the Sunday meals, the foods were raw so that the parents would cook them fresh on Sunday. The meals of lunch and dinner were the same for all participants. For the breakfast, morning and afternoon snacks, children could choose based on a list of available products before the beginning of the organic period. Participants crossed over to the alternate diet on the following day after the first period was completed. A washout period was not required; it was intrinsically included in the two periods, since the first urine sample of the second period was collected about 12 days after the beginning of the second period and the pesticides half-lives are short (half-life for pyrethroids is less than 12 h and those for neonics range from 5-33 hours), so no carryover effect was expected.

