During the conventional period, participants were asked to maintain their usual dietary habits and choices (>80% conventional diet) for a total of maximum 40 days. The organic period was organized in two 20-day cycles with differences in the menu to allow for greater variety in the meals, so that the participants' compliance to the organic diet would be enhanced. During the organic period, participants were asked to strictly consume the two organic dietary menus provided to them for a total of 40 days. The organic dietary menus were prepared by a certified dietitian based on EFSA energy requirements for children aged 10-12 years,¹ and included five meals per day; breakfast, morning snack, lunch, afternoon snack, and dinner. The meals of the organic period were delivered to schools Monday to Saturday, except for Sunday. Upon arrival of daily meals to each school, the teachers and headmaster were responsible for handing the packages to each participating child, using a project participant list around lunch time. On Saturday, the food package included both the Saturday and Sunday meals; for the Sunday meals, the foods were raw so that the parents would cook them fresh on Sunday. The meals of lunch and dinner were the same for all participants. For the breakfast, morning and afternoon snacks, children could choose based on a list of available products before the beginning of the organic period. Participants crossed over to the alternate diet on the following day after the first period was completed. A washout period was not required; it was intrinsically included in the two periods, since the first urine sample of the second period was collected about 12 days after the beginning of the second period and the pesticides half-lives are short (half-life for pyrethroids is less than 12 h and those for neonics range from 5-33 hours), so no carryover effect was expected.^{2,3}

Each participant provided maximum six first morning urine samples during the whole duration of the 2-period study; one baseline sample, two samples in the conventional period, and three samples in the organic period. Anthropometric measurements (weight, height, and waist circumference) were taken at the beginning of the study, at the end of the organic period, and at the end of the study (for Group 2, the end of study and end of organic period was the same time point) by trained researchers at the school

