The change in outcomes (biomarkers of pesticide exposure and of oxidative stress) between the baseline and the end of the organic period was assessed with the percent change between the last sample of the conventional treatment period (before the start of the organic treatment) and the last urine sample of the organic treatment period. The percent change was estimated only for the participants who completed the full course of the organic treatment. A one-sample T-test was used to assess whether the percent change was significantly different than zero.

Overall change between conventional and organic period

The overall change in outcomes between the conventional and organic period was assessed using the overall difference in median levels. The conventional period consists of all conventional samples, including the baseline sample, and the organic period will consist of all organic samples for all participants, regardless of the duration for which they followed the organic treatment. The overall difference in the median levels of the outcomes between the conventional and the organic period was assessed using the unpaired T-test if the outcomes were normally distributed or using the non-parametric Wilcoxon test if the outcomes were non-normally distributed.

Primary analysis of outcomes

Linear mixed-effect regression models were used for continuous outcomes and logistic models for binary variables (i.e. those with >70% values below LOD), to account for the duration and the effect of treatment. To account for the clustering of participants within schools and the repeated measures within person, the models will include student-level and school-level random intercepts with unsupervised covariance matrix. Fixed effects were: the treatment condition (organic or conventional) and time (days of treatment, where time=0 was the start of the treatment). An interaction term for the treatment condition and time were considered and dropped when not meeting the threshold of p-value=0.05. The models were adjusted for the baseline value of the outcome in order to account for the background biomarker levels of the participant. The baseline sample was a conventional sample for both groups but it was not consecutive to the conventional phase due to the study design and, thus, it is indicative of each participants exposure prior to participation in the study

In all regression models, the continuous variables, other than time, were centred at the population means.

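### Two supporting organic-versus-conventional tests and the post-hoc BMI SDS model cannot fully separate organic diet from calendar time

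*SAP*

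**What the plan says.** **Percent change.** The SAP (Change between baseline and the end of the organic period) takes "the percent change between the last sample of the conventional treatment period (before the start of the organic treatment" as the reference, compares it with the last organic sample, and applies a one-sample t-test against zero. Protocol item 12 agrees: "The percent change between the baseline (last sample of conventional treatment before the start of the organic treatment".

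**Pooled comparison.** In the SAP (Overall change between conventional and organic period), "The conventional period consists of all conventional samples, including the baseline sample". The difference from all organic samples "was assessed using the unpaired T-test if the outcomes were normally distributed", and otherwise by a Wilcoxon test. Protocol item 12 says the change "was determined using Wilcoxon test for all biomarkers (non-normal variables". Neither document names the Wilcoxon version or mentions school or period for this test.

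**BMI SDS.** Anthropometry was taken at study start, at the end of the organic period and at study end; for Group 2 the last two coincide (Protocol item 5; SAP, Intervention). The BMI SDS analysis uses only study start and end of organic (Protocol item 6a). The SAP (Post-hoc analysis) also limits it to two timepoints and presents the models as describing what organic diet does to BMI SDS.

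**Timing.** Protocol item 3a plans 40 days of each diet and reports a Group 1 to Group 2 ratio of 1:2.5; item 6a refers to an 80-day trial. The SAP says participants kept their usual diet "for a total of maximum 40 days". Each child gave at most one baseline, two conventional and three organic samples. The baseline sample is undated; the SAP says "it was not consecutive to the conventional phase due to the study design".

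**The concern.** A crossover protects against calendar effects because one sequence takes the treatment early and the other takes it late, so a trend pushes the two within-child differences in opposite directions. Each of these three analyses gives up some or all of that protection.

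- The percent change always looks backward, so both sequences push the same way.
- The pooled test keeps both orders, but weights them 1:2.5 and adds an early sample to the conventional side only.
- The BMI SDS window for Group 2 contains the comparator diet as well as the organic diet.

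The first two attach significance tests to the primary and secondary biomarkers, and the third carries a causal description. A reader could take all three as independent support for the primary model.

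**Working it through.** The plan gives no numerical figure for these analyses. Its sample size of 200 does reproduce ((1.960 + 0.842) × 0.5/0.1)² = 196.2, and is not in dispute.

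**Inputs.** Shares of children from 1:2.5 are 1/3.5 = 0.286 (Group 1) and 2.5/3.5 = 0.714 (Group 2). Both periods last 40 days as planned. Assumed: baseline at day 0; organic samples on days 12, 26 and 40 of the period; conventional samples on days 12 and 40. The documents support only the first of these for period 2: "the first urine sample of the second period was collected about 12 days after the beginning of the second period". Drift is expressed in units of one 40-day drift.

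**(1) Percent change.** Group 1 runs from baseline (day −g) to day 40; Group 2 runs from day 40 to day 80.
- Drift counted as diet = 0.286 × (40 + g)/40 + 0.714.
- g = 0 gives 1.00. If baseline was 14 or 30 days before the start (assumed range), it is 1.10 or 1.21.

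**(2) Pooled comparison, share of a calendar effect that enters.**
- Step between periods, baseline at period-1 level: Group 2 contributes +1 and Group 1 −2/3, so 0.714 − 0.286 × 2/3 = 0.52.
- Linear drift, Group 1: mean organic day 26 minus mean conventional day (0 + 52 + 80)/3 = 44 gives −18.0. Group 2: 66 − (0 + 12 + 40)/3 = +48.7. Total (0.714 × 48.7 − 0.286 × 18.0)/40 = 0.74.

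**(2) Pooled comparison, error rate.** Take 200 children, three samples per diet, total variance 1, within-child correlation ρ and an unpaired or rank-sum test (all assumed apart from the planned 200). The nominal variance is 2/600. Child and school levels cancel within child, so with no school-by-period variance the true variance is (1 − ρ) × 2/600 and the true level is 2Φ(−1.96/√(1 − ρ)).
- ρ = 0.3: 1.9%. ρ = 0.5: 0.6%. A rank-sum simulation gave 2.1% and 0.5%.
- With school-by-period variance w (share of total), three schools per sequence and baseline counted in period 1, the true variance is (1 − ρ − w) × 2/600 + wK, where K = 3(0.286/3)² × 8/9 + 3(0.714/3)² × 2 = 0.364. It equals the nominal variance at w = ρ(2/600)/(K − 2/600) = 0.0028 (ρ = 0.3) or 0.0046 (ρ = 0.5). With baseline as its own period, K = 0.307 and the values are 0.0033 and 0.0055.

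**What drift would do to (1) and (2).** Simulation with no diet effect: 150 children, three schools per sequence, log-scale SDs of 0.5 between children, 0.7 within child and 0.1 between schools, no school-by-period variance, 1,000 runs (all assumed).

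| Drift over 80 days (log units) | Percent change: apparent effect, rejections | Pooled rank-sum: apparent effect, rejections |
|---|---|---|
| 0 | 0.00, 5% | 0.00, 2% |
| −0.1 | −0.05, 9% | −0.04, 5% |
| −0.2 | −0.10, 23% | −0.07, 20% |
| −0.4 | −0.20, 67% | −0.15, 75% |

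**(3) BMI SDS.** Group 2's window is 80 days, of which 40/80 = 50% is conventional diet. Over all children the conventional share of child-days is 0.714 × 40/(0.714 × 80 + 0.286 × 40) = 28.6/68.6 = 42%.

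**The case against.** **These are not the primary analysis.** True. Both tests sit outside the primary mixed model and outside the false-discovery-rate family, which covers regression parameters only, and their headings speak of change. A reader might infer that the primary result is biased for these reasons; that does not follow. Equally, the primary model does not clearly repair these comparisons: its time variable is days within treatment, and no period term is stated.

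**No drift is shown.** Also true. A reader might infer that the reported changes are seasonal. Nothing in the documents says so, and the drifts tabulated above are hypothetical.

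**The pooled test may be conservative.** This stands. The sample-size sections assume equal within-period and between-period intracluster correlations, which amounts to no school-by-period variance. On that footing the test rejects too rarely. A reader might infer inflated false positives, but that needs a variance the documents do not give. Nor does the pooled test wholly confuse diet with time, since the leakage is partial. Whether it ignores the child depends on the unnamed Wilcoxon version: rank-sum is likely, given the unpaired t-test beside it, while a signed-rank test would use the child but still not school or period.

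**The conventional period might have been shorter.** The SAP's upper-limit wording invites that inference, but the Protocol plans 40 days and an 80-day trial, so no shorter length is used here.

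**BMI SDS is already qualified.** Protocol item 6a calls it post hoc and concedes uncontrolled calories and habits. The measurement schedule is openly stated, and standardisation removes expected growth. None of this addresses Group 2's two-diet window.

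**Conclusion.** The point holds for all three analyses, as a limit on what they can show.

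- Percent change: the organic sample is later for every child. All of a linear 40-day drift is counted, given 40-day periods, baseline near day 0 and last samples near period end.
- Pooled comparison: about 52% of a step period effect and about 74% of a linear drift enter, the latter under the assumed sample days. The nominal 5% is really about 2% to 0.6% for ρ of 0.3 to 0.5 with no school-by-period variance. It becomes liberal only if that variance exceeds roughly 0.3% to 0.5% of the total.
- BMI SDS: half of Group 2's planned window, and about 42% of all child-days, is conventional diet. This needs no drift assumption. Group 1's third measurement, the only one that isolates a conventional period, goes unused.

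**What to change.** 1. **Percent change.** Keep it as an uncontrolled before-after description without a p-value. Optionally add the within-child log difference between the last organic-period and last conventional-period sample in both groups, averaging the two sequence means with equal weight. Base any p-value on school means. With equal periods this removes both a step and a linear trend. State its price:
   - It assumes no carryover into Group 1's conventional period. The documents support that with half-lives for the pesticides only, not for 8-iso-PGF2a, MDA or 8-OHdG.
   - Equal weighting raises child-level variance by about 22%: 0.25 × (3.5 + 1.4) = 1.225.
   - Six schools in two sequences leave 4 degrees of freedom (critical value 2.78 instead of 1.96).
2. **Pooled comparison.** Show medians by diet and sequence as description, without a p-value.
3. **BMI SDS.** Report Group 1's organic-period and conventional-period changes from all three measurements. Report Group 2's as one combined two-diet change; no existing measurement can split it. Withdraw the wording that attributes the BMI SDS result to organic diet.

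The cost is minor re-analysis of data already collected, or relabelling alone for items 1 and 2. The percent-change and BMI statements will be weaker.
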